# 6.1.3 Day 3 (± 1 day) – Safety Telephone Contact

• Using an Institutional Review Board (IRB)-approved script, the trial staff will contact the subjects using a telephone call to query for any grade 3 solicited or unsolicited adverse event or SAE experienced since their last visit, and any concomitant medications taken for these events. Subjects may be asked to return to the clinic for an unscheduled visit to evaluate the event(s) at the trial investigator's discretion.

# 6.1.4 Day 7 (+1 day) – Safety Follow-up Visit for (Stage 1 Subjects ONLY)

All Stage 1 subjects will return to the clinic on approximately Day 7 for the following procedures:

- Vital sign collection (heart rate, blood pressure, respiratory rate, and oral temperature).
- Review and collection of subject diary.
- Interval history to query for any unsolicited AEs, including MAEs, SNMCs, or SAEs, occurring since the last trial visit, and any concomitant medications taken. A directed physical examination may be performed at the investigator's discretion to evaluate any AEs.
- Schedule the Day 21 visit.

# 6.1.5 Day 7 (± 1 day) – Safety Telephone Contact (Stage 2 Subjects ONLY)

• Using an IRB-approved script, the trial staff will contact the subjects using a telephone call to query for any grade 3 solicited or unsolicited adverse event or SAE experienced since their last telephone contact, and any concomitant medications taken for these events. Subjects may be asked to return to the clinic for an unscheduled visit to evaluate the event(s) at the trial investigator's discretion.

# 6.1.6 Day 21 (± 2 days) – Injection 2 Visit

All subjects will return to the clinic on approximately Day 21 for the following procedures:

- Vital sign collection (heart rate, blood pressure, respiratory rate, and oral temperature).
- Review and collection of subject diary (Stage 2 subjects ONLY).
- Interval history to query for any unsolicited AEs, including MAEs, SNMCs, or SAEs, occurring since the last trial visit, and any concomitant medications taken. A directed physical examination may be performed at the investigator's discretion to evaluate any AEs.
- Blood draw for immunogenicity assessments (20 mL) and clinical safety assessments (10 mL).

- Alcohol swab cleansing of the injection site followed by IM injection into the dominant deltoid of a licensed seasonal influenza vaccine (using the manufacturer's instructions) for Group A and B subjects only, and of saline placebo for Group C subjects only. Note that if only the non-dominant deltoid is available for the injection, it is acceptable to inject the assigned trial treatment into the non-dominant deltoid. Subjects should be free of acute illness (defined as the presence of a moderate or severe illness with or without fever, or an oral temperature ≥ 38.0°C) in order to receive the second vaccination. Subjects presenting with an acute illness on Day 21 may return to the study site within the next 7 days to receive their 2nd vaccination. If a subject has experienced any AEs/SAE between study Days 0 and 21, then Day 21 vaccination may be administered or delayed for up to 7 days based on the Investigator's discretion.
- Monitoring for any AEs for 30 60 minutes following vaccination.
- Post-injection vital sign collection (heart rate, blood pressure, respiratory rate, and oral temperature) at 30 60 minutes following vaccination.
- Schedule the Day 56 visit.

#### 6.1.7 Day 56 (± 2 days) – Follow-up Visit

At Day 56, all subjects will return to the clinic for the following procedures:

- Vital sign collection (heart rate, blood pressure, respiratory rate, and oral temperature).
- Interval history to query for any MAEs, SNMCs, or SAEs occurring since the last trial visit, and any concomitant medications taken for these events. A directed physical examination may be performed at the investigator's discretion to evaluate any AEs.
- Schedule the Day 90 telephone contact and the Day 182 in-clinic visit.

#### 6.1.8 Day 90 (± 7 days) – Safety Telephone Contact

• Using an IRB-approved script, the trial staff will contact the subjects using a telephone call to query for any MAEs, SAEs, and SNMCs since their last visit, and any concomitant medications taken for these events.

#### 6.1.9 Day 182 (± 7 days) – Follow-up Visit

At Day 182, all subjects will return to the clinic for the following procedures:

- Vital sign collection (heart rate, blood pressure, respiratory rate, and oral temperature).
- Interval history to query for any MAEs, SNMCs, or SAEs occurring since the last telephone contact, and any concomitant medications taken for these events. A directed physical examination may be performed at the investigator's discretion to evaluate any AEs.
- Schedule the Day 273 telephone contact and the end of the trial visit (Day 364) in-clinic visit.

#### 6.1.10 Day 273 (± 7 days) – Safety Telephone Contact

• Using an IRB-approved script, the trial staff will contact the subjects using a telephone call to query for any MAEs, SAEs, and SNMCs since their last visit, and any concomitant medications taken for these events.

# 6.1.11 Day 364 (± 14 days) - Follow-up Visit

At Day 364, all subjects will return to the clinic for the following procedures:

- Vital sign collection (heart rate, blood pressure, respiratory rate, and oral temperature).
- Interval history to query for any MAEs, SNMCs, or SAEs occurring since the last telephone contact, and any concomitant medications taken for these events. A directed physical examination may be performed at the investigator's discretion to evaluate any AEs.
- This visit will mark the end of the trial for the subjects.

# 6.2 Unscheduled Visits

Unscheduled visits are defined as any visits performed to the site outside of the regular visit schedule and can occur at the investigator's discretion for any other trial procedures deemed necessary. Subjects will be encouraged to notify the investigator if any severe (grade 3) local or systemic solicited AEs occur within the 7-day post-dosing period (eg, from Day 0 through Day 6), or if any severe, serious, or otherwise concerning AEs occur at any time following dosing. If symptoms are presented that would require a physical exam to adequately assess potential AEs, the exam should be performed and vital signs collected.

# 6.3 Concomitant Therapy

Subjects may receive all concomitant medications and procedures deemed necessary to provide adequate healthcare during the trial, with the exception of those specified in the exclusion criteria. Routine medical standards of care are permitted, including vaccines needed for emergent indications (eg, tetanus booster in response to a penetrating injury). Routine (ie, non-emergent) vaccinations are permitted for all subjects after completion of the Day 21 trial visit.

Concomitant medications, procedures, and hospitalizations will be recorded throughout the trial including the period from the day informed consent is obtained through the end of trial follow-up. All new or changed concomitant medications taken through Day 21 will be recorded; thereafter, only concomitant medications taken for MAEs, SNMCs, or SAEs will be recorded. The investigator will document the reason for use of the concomitant medication.

# 6.4 Declining Trial Treatments or Procedures

Subjects have the right to decline trial treatment or other trial procedures for any reason at any time during the trial. This trial contemplates 2 injections containing either Tri-NIV with Matrix-M1 adjuvant, Fluzone HD, or saline placebo. Refusal of the investigational test article on Day 0 constitutes trial withdrawal without exposure, and no further follow-up is required. If a subject declines trial procedures subsequent to receipt of the investigational product, it should be recorded as a protocol deviation and the reason should be clearly documented in the source

document. The subject will be asked to complete all other trial procedures as applicable. If the subject does not wish to remain in the trial, the subject can choose to withdraw consent and discontinue at any time as outlined in Section 6.5.

The investigator may, at his/her discretion, restrict a subject from receiving trial treatment or other trial procedures if he/she considers it to be in the subject's best interest to do so, but can suggest that the subject remain in the trial to be followed for safety if the subject has received a test article. In this situation, the reason for not performing the trial treatment and/or procedure should also be recorded as a protocol deviation and clearly documented in the source document.

# 6.5 Premature Discontinuation from Trial

Subjects who provide consent but are found to be ineligible on screening will be informed of the reason for ineligibility and may be provided with local medical referral by the investigator as appropriate, but will receive no further trial follow-up.

Subject participation in the trial is strictly voluntary. Subjects have the right to withdraw from the trial at any time and for any reason, without penalty. The investigator may also, at his/her discretion, discontinue subjects from the trial if he/she considers it to be in the participant's best interest to do so, or if the subject is not willing or able to comply with the trial requirements. Novavax will be notified immediately by the investigator if a subject prematurely ends trial participation. The reason for early discontinuation will be clearly documented in the electronic case report form (eCRF). A withdrawal due to an AE will initiate additional reporting requirements as outlined in Section 8.3.

In the event of early termination, investigators will make every reasonable effort to perform trial completion procedures. Trial completion procedures will include a query for any MAEs, SNMCs, or SAEs occurring since the last trial visit, and any concomitant medications taken to treat these events, as well as a blood draw for serology testing (20 mL) and clinical safety laboratory testing (10 mL) if prior to the Day 21 trial visit. Subjects that terminate from the trial early will not be replaced.

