# 3.2 Trial Endpoints

## 3.2.1 Primary Endpoints

- Number and percentage (95% confidence intervals [CI]) of subjects with solicited local and systemic adverse events over the 7 days post-injection (ie, Day 0 through Day 6 post-dosing); all adverse events (including adverse changes in clinical laboratory parameters) through 21 days post-injection; and MAEs, SAEs, and SNMCs through 1 year post-Day 0 dosing. Note: The 21 day post vaccination all adverse event profile will include all unsolicited AEs reported from test article receipt until the day preceding the rescue dose, ie, events with onset dates between days 0 to 20 for subjects who receive the rescue dose as scheduled on day 21. Rules for defining the dataset in subjects who receive the rescue dose before or after day 21, or no rescue dose, are detailed in the statistical analysis plan.
- Antibody titers specific for the HA receptor binding domains of each of the virus strains included in Tri-NIV as measured by the HAI assay at Day 0 pre-dosing and Day 21 post-dosing . Derived/calculated endpoints based on these data will include:
  - Geometric mean titer (GMT) defined as the antilog of the mean of the log-transformed HAI titers for a given treatment group.
  - $\circ$  Geometric mean ratio (GMR) defined as the ratio of post-vaccination and pre-vaccination HAI GMTs within the same treatment group (designated as GMRPost/Pre).
  - Seroconversion rate (SCR) defined as the percentage of subjects with either a baseline HAI titer < 1:10 and a post-vaccination titer  $\geq$  1:40, or a baseline HAI titer  $\geq$  1:10 and a 4-fold increase in post-vaccination HAI titer relative to baseline.
  - Seroprotection rate (SPR) defined as the percentage of subjects with an HAI titer  $\ge 1:40$ .

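### Subjects who leave before Day 21 or miss that visit entirely are asked only about MAEs, SNMCs and SAEs, with no diary collection, contrary to the protocol's own all-AE rule through Day 21

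*Protocol*

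**What the plan says.** Protocol 3.2.1 makes two short-term safety measures primary: solicited events over Days 0-6, and "all adverse events (including adverse changes in clinical laboratory parameters) through 21 days post-injection". Collection for these measures differs by stage.

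- **Stage 2, Day 3 and Day 7 calls (6.1.3, 6.1.5).** These ask only about severe and serious events. The Day 7 script is a "query for any grade 3 solicited or unsolicited adverse event or SAE experienced since their last telephone contact".
- **Stage 2, Day 21 visit (6.1.6).** This is the first scheduled question about all events after discharge on Day 0: "Interval history to query for any unsolicited AEs, including MAEs, SNMCs, or SAEs, occurring since the last trial visit, and any concomitant medications taken". It is also where the diary is handed in.
- **Stage 1, Day 7 visit (6.1.4).** The diary is reviewed and collected, and all unsolicited events are asked about.

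For a subject who terminates early, 6.5 states: "Trial completion procedures will include a query for any MAEs, SNMCs, or SAEs occurring since the last trial visit". Medications are limited to those taken for such events. The section foresees termination before Day 21, because it continues "as well as a blood draw for serology testing (20 mL) and clinical safety laboratory testing (10 mL) if prior to the Day 21 trial", but it neither widens the event query nor mentions the diary. For a subject who misses Day 21 and next comes to the clinic on Day 56, 6.1.7 prescribes: "Interval history to query for any MAEs, SNMCs, or SAEs occurring since the last trial visit, and any concomitant medications taken for these events". Appendix 1 shows no diary review after Day 21.

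Three other places set a broader standard. Appendix 1 note [4] has all adverse events and concomitant medications collected through Day 21. Section 8.1 has all classes of event collected through 21 days, at scheduled visits. Section 6.3 has all new or changed medications recorded through Day 21.

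**The concern.** For most of the trial, both short-term primary safety measures depend on one visit. If that visit does not happen, the procedures that replace it ask a narrower question than the endpoint needs. A site that follows 6.5 or 6.1.7 literally will not ask about a mild headache on Day 4 or a moderate, untreated event on Day 12, and will not ask for the diary.

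The events at risk are grade 1-2 and not medically attended, which is where most reactogenicity lies. In the sponsor's RSV F older-adult trial described in Protocol 1.9, short-term reactogenicity after one Matrix-M1-adjuvanted dose was 40 to 60%, while severe solicited events were 0 to 4%. That is a different antigen, so it only illustrates the point: telephone calls limited to grade 3 events see little of the profile.

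These subjects stay in the analysis. The SAP's Safety Population keeps everyone dosed on Day 0, and SAP 8.1.2 gives a subject without a rescue dose a window of Days 0 to 22. The analysis therefore expects data that the collection procedures do not seek. In a first-in-human trial of this formulation, leaving early or skipping a visit could be related to tolerability.

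**Working it through.** **1. What is scheduled for a subject who never attends Day 21**

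| | Stage 2 | Stage 1, attended Day 7 |
|---|---|---|
| Diary, Days 0-6 | no scheduled collection | collected at Day 7 |
| All unsolicited AEs up to Day 7 | not asked | asked at Day 7 |
| All unsolicited AEs after Day 7 | not asked | not asked |
| Grade 3 events and SAEs | Day 3 and Day 7 calls | Day 3 call and Day 7 visit |
| MAEs, SNMCs, SAEs | termination contact or Day 56 | termination contact or Day 56 |
| Safety bloods, if terminating before Day 21 | drawn | drawn |

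Stage 2 is 270/330 = 82% of subjects. A subject who terminates after attending Day 21 loses nothing from either endpoint.

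**2. The plan's own precision figures (Protocol 10.5, SAP 9)**

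Probability of at least one event = 1 - (1 - p)^n. Upper 95% one-sided bound with zero events = 1 - 0.05^(1/n).

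- n = 110, p = 2.1%: 90.3%; bound 2.69% (stated: over 90%, 2.7%).
- n = 220, p = 1.1%: 91.2%; bound 1.35% (stated: over 90%, 1.4%).

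Both reproduce. They assume that every subject was asked about the event.

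**3. Effect on those figures, for events the narrow queries would not capture**

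The documents say only that some subjects will not complete, so the share d without ordinary-AE data is an assumption.

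| d | n per arm | P(at least one) at 2.1% | n combined | P(at least one) at 1.1% |
|---|---|---|---|---|
| 1% | 109 | 90.1% | 218 | 91.0% |
| 2% | 108 | 89.9% | 216 | 90.8% |
| 5% | 104 | 89.0% | 209 | 90.1% |
| 10% | 99 | 87.8% | 198 | 88.8% |

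**4. Effect on a common event rate**

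Assume a true 21-day rate of 50%, d of 2-5% (0.02 x 110 = 2.2 to 0.05 x 110 = 5.5, about 2 to 6 per arm), and nothing captured from these subjects.

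- *Kept in the denominator as event-free, loss unrelated to events:* 50% x (1 - d) = 49.0% to 47.5%, a shortfall of 1.0 to 2.5 points.
- *Kept as event-free, and every one of them had an event:* 50% - d = 48% to 45%, a shortfall of 2 to 5 points.
- *Removed from the denominator, loss unrelated to events:* no bias, only a smaller n.
- *Removed, and every one of them had an event:* (0.50 - d)/(1 - d) = 0.48/0.98 = 49.0% to 0.45/0.95 = 47.4%, a shortfall of 1.0 to 2.6 points.

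A denominator rule alone therefore does not remove the problem if leaving is related to events; the data have to be collected. The unrelated-loss shortfall scales with the true rate: at 30% it is 0.3 points for d = 1% and 3 points for d = 10%.

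**5. Scale**

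The 95% half-width for 50% with n = 110 is about 1.96 x sqrt(0.25/110) = 9.3 points, so the shortfall is smaller than the sampling error of one arm.

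**The case against.** The strongest reply is that the protocol already intends full collection. Appendix 1 note [4], 8.1 and 6.3 all set the standard at all events or medications through Day 21; the list in 6.5 is not said to be exhaustive; and SAP 12.4 encourages withdrawn subjects to return for scheduled assessments. Severe events reported by telephone are entered promptly (8.1.1, 8.1.2), subjects may report spontaneously or attend unscheduled visits, and SAP 3.4.1 flags a diary that was not returned.

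Most of this stands as a limit on the finding. A reader might infer that these subjects' adverse events are certain to be lost. The documents do not support that: the general rule keeps such events in scope if they are reported. What fails is the written route. Section 8.1 ties collection to scheduled visits, the relevant visit is the one missed, and the next one asks the narrow question. A compliance flag records that a diary is absent but does not retrieve it.

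A reader might also infer that the analysis counts these subjects as free of events. The SAP sets no such rule. SAP 8.1 reports percentages of subjects in each treatment group, and SAP 12.5 makes no substitutions, which leans that way; but SAP 12 calls for a missing-data category in categorical tabulations.

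Two further inferences go too far. Stage 1 subjects who attend Day 7 do not lose their 7-day data. Different bias between arms is possible but rests on nothing stated.

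Finally, the effect is small, rests on assumed rates, and arises in a descriptive trial without planned hypothesis tests. That is fair, and it limits the weight of the point.

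**Conclusion.** The inconsistency is real and narrow. For subjects who terminate before the Day 21 visit or miss it entirely, Protocol 6.5 and 6.1.7 prescribe a narrower event and medication query than note [4], 8.1 and 6.3 require, and no diary collection. In Stage 2 this leaves no scheduled source for grade 1-2, non-attended events in either short-term primary safety endpoint. In Stage 1, after an attended Day 7 visit, only later unsolicited events are exposed. Severe, serious and medically attended events, and the laboratory data taken at termination before Day 21, are still sought.

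The size is modest: about 1-2.5 points on a 50% rate, or 2-5 points in the extreme case. This rests on three assumptions that the documents do not settle: 2-5% of an arm affected, a 50% true rate, and these subjects kept as event-free with nothing captured from them. It does not undermine the trial, but it concerns primary endpoints, and events that nobody asked about are hard to recover later.

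**What to change.** - **Protocol 6.5.** For termination before the Day 21 visit, ask about all adverse events and all new or changed concomitant medications since the last visit, and collect any outstanding diary. The reference point should be the last visit, not the last contact, because the Stage 2 calls ask only about grade 3 events and SAEs.
- **Protocol 6.1.7, or the first contact after a missed Day 21.** Do the same for events with onset in the SAP 8.1.2 window, which runs through Day 22 when no rescue dose was given. A cut-off at Day 20 or 21 would leave part of that window unasked.
- **SAP 8.1.** Report the solicited and 21-day percentages with the number of subjects with data shown, and state how subjects without data are counted.

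The cost is two protocol sentences, an eCRF prompt and a column in the tables. Subjects who return late must recall further back, and nothing is recovered from those who refuse all contact.

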# 6.6 Protocol Deviations

A protocol deviation (PD) will be defined as a failure to comply with the requirements set forth in the protocol. While the majority of PDs will be self-reported by the clinical sites in the electronic case report form (eCRF), in certain instances PDs may also be determined programmatically through the course of the trial. Examples of both types of PDs are provided in Table 2.

Self-reported PDs	Programmatically-determined PDs	
Excluded Concomitant Medication or Procedure	Missed Visit	
Inclusion / Exclusion Criteria	Out of Window Visit	
Informed Consent	Trial Procedure Not Done	
Vaccination Error	Randomization Error	

Table 2:Protocol Deviations

#### Table 2:Protocol Deviations

Self-reported PDs	Programmatically-determined PDs
Other 	Diary Compliance

 PDs that do not belong under any pre-specified category will be categorized as "Other" using an open-text field.

# 6.7 Trial Termination

Novavax reserves the right to terminate the trial at any time for any reason. If and when the trial is terminated (either prematurely or as scheduled), the investigator will notify the IRB for the trial and other authorities, as required by local regulatory requirements.

The scheduled end of the trial will be the completion of the last Day 364 follow-up visit with the last trial subject.

# 7 TRIAL LABORATORY REQUIREMENTS

Appendix 3 specifies the maximum amount of blood (up to 60 mL) to be drawn for safety laboratory assessments and immunogenicity laboratory assessments to be completed throughout the trial.

# 7.1 Clinical Laboratory Testing

The following laboratory tests will be performed by a qualified central laboratory designated by Novavax on blood samples collected from subjects on Days 0 and 21.

• Serum chemistry – alanine aminotransferase (ALT), aspartate aminotransferase (AST), total bilirubin, alkaline phosphatase (ALP), creatinine, and blood urea nitrogen (BUN).

Hematology – complete blood count (CBC) with hemoglobin, hematocrit, red blood cell (RBC) count, platelet count, and white blood cell (WBC) count with differential.

# 7.2 Serological Assessments of Immunogenicity

Immunogenicity assessments will be made on subject sera collected on Days 0 and 21. The primary measure of immunogenicity for the trial is HAI titers specific for the HA receptor binding domains of each of the virus strains included in Tri-NIV. The secondary and /exploratory variables of immunogenicity include HAI titers specific for the HA receptor binding domains of at least 2 historic A virus strains (one H1N1 and one H3N2), and a representative of the B/Yamagata lineage; and neutralizing antibody titers specific for the virus strains included in Tri-NIV and the Fluzone HD comparator, as well as selected historical strains and a B/Yamagata strain. In addition, exploratory measures of immunogenicity also include antibodies competitive with broadly-neutralizing monoclonal antibodies to HA of varying specificities, as measured by competitive-binding in a biosensor assay.

